### **8.3 Exploratory Endpoints**

8.3.1 To compare the Cumulus vs. Volpara vs. LIBRA breast density measurement methods to estimate percent change in mammographic breast density from baseline to Month 12 in women applying 2mg of 4-OHT gel per breast vs. placebo.

8.3.2 To perform correlation of drug concentrations in the plasma and the tissue.

8.3.3 To evaluate plasma measurements of Insulin-like growth factor (IGF) pathway members, C-reactive protein (CRP), and estradiol.

8.3.4 To compare the 2D natural vs. 2D synthetic breast density measurement using the Cumulus method to estimate percent change in mammographic breast density from baseline to Month 12 in women applying 2mg of 4-OHT gel per breast vs. placebo.

8.3.5 To evaluate tissue biomarkers (among women undergoing optional pre- and post-treatment biopsies):

- Structure-function activity of TLDUs will be evaluated by counting acinar density.
- Breast tissue density will be evaluated by assessing the patterns of collagen matrix.
- Hormone-mediated cellular activity will be evaluated by measuring the transcriptional expression levels of ER-alpha and ER-associated genes (SETER/PR index).
- Pharmacogenomic response to 4-OHT will be evaluated by measuring Ki67 protein by immunohistochemistry and aurora kinase-alpha gene expression.
- Inflammatory response to 4-OHT therapy will be evaluated by measuring COX2 and p16 proteins, and recruitment of CD68 monocytes by immunohistochemistry.

8.3.6 To examine whether any reductions in mammographic density seen after 1 year of 4-OHT vs. placebo gel application persist at 24 months (or longer under the COVID-19 Contingency Plan), one year after gel application has stopped.

## 8.4 Off-Agent Criteria

Participants may stop applying the study gel for the following reasons: completed the protocol-prescribed intervention, adverse event or serious adverse event, inadequate agent supply, noncompliance, concomitant medications, medical contraindication, or pregnancy. Participants will continue to be followed, if possible, for safety reasons and in order to collect endpoint data according to the schedule of events. We plan to accrue 7 more participants per arm to account for women who are not evaluable because they discontinued participation prior to meeting criteria for contributing evaluable results. Women who discontinue the agent for any reason should continue on study if possible to allow for collection of their routine mammograms.

## 8.5 Off-Study Criteria

Participants may go ‘off-study’ for the following reasons: the protocol intervention and any protocol-required follow-up period is completed, adverse event/serious adverse event, lost to follow-up, non-compliance, concomitant medication, medical contraindication, withdraw consent, or death. Participants found to be ineligible during the screening phase and after signing the Informed Consent document and assigning the PID number, will be considered “screen failures”. Such participants will be taken off study and the appropriate end of study CRFs will be completed for these participants.

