### 13.4 Primary Objective, Endpoint(s), Analysis Plan

The primary objective of this study is to evaluate the change in percent MD (using Cumulus software) from baseline to the week 52 in women applying 4 mg OHT gel versus placebo based on the intent-to-treat principle. The intent-to-treat population is defined as all participants who are randomized and have MD measurements from both baseline and 52 weeks. The primary analysis will be performed comparing the active group versus placebo group per randomization, regardless of the compliance of each participant.

The percent MD is the MD (percent dense area) that is visually estimated using both the mediolateral oblique (MLO) view and the craniocaudal (CC) view as the proportion of the total breast area that was composed of dense tissue (to the nearest 5%). For the study purpose, the densest breast will be the target lesion for the primary endpoint. Breast biopsy for secondary and exploratory endpoints will be performed in the opposite (non-target) breast.

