At the end of the study, all participants who have MD measurements from both baseline and 52 weeks, regardless of the compliance, will be included in the primary analysis. Change in percent MD of the breast from baseline to 52 weeks will be summarized using descriptive statistics, such as mean, standard deviation, median and range for each arm. With visual assessments of MD from both the MLO and CC views for evaluating the primary endpoint, Hotelling's  $T^2$  test will be used to conduct multivariate hypothesis testing which includes both views. Hotelling's  $T^2$  test represents the multivariate generalization to the independent two-sample t-test in the univariate setting. The correlation and variance-covariance matrix will be assessed to estimate the level of dependency between the MLO and the CC views. The mean change in percent MD at 52 weeks incorporating both the MLO and CC views will be compared between the two groups utilizing Hotelling's  $T^2$  test. Q-Q plots, used to visually assess the assumption of normality, will be constructed for the marginal distributions associated with observations emanating from both the MLO and the CC view. Assuming the mean difference in density between the observations between the 4-OHT and the placebo groups is approximately normally distributed, then the primary analysis will be conducted as previously described. Additionally, a 95% confidence ellipse (simultaneous confidence intervals) for the mean vector containing information from both views will be provided. If the change in density is not normally distributed, then we will try to rescale to achieve approximate normality by using the Box-Cox transformation. In our prior experience evaluating change in density in response to oral tamoxifen, change in density was scaled and raised to the 1.75th power to approximate normality. We will have to determine what power to use in the Box-Cox transformation based on the data that we have on hand. Transformations may be performed when necessary to make the measure of MD close to normal distribution before evaluating the change of MD over time between two groups. If the Hotelling's  $T^2$  test is significant, we will further examine whether the significant difference between the 4-OHT gel group and the placebo group is in the MLO view or the CC view or both. Note that the sample size calculation is based on the two-sample t-test. It provides a conservative estimate of the statistical power because the Hotelling's  $T^2$  test is more efficient than the two-sample t-test.

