### **13.6 Reporting and Exclusions**

Every reasonable attempt will be made to recover any missing data. If any data for the primary efficacy measure remains missing, then the change of the primary endpoint will not be calculated, and the participant will not be evaluable for the primary endpoint. We will also consider multiple imputations using predictive values based on regression models under the assumption of missing at random to supplement the primary analysis. In addition, any available data will be included in the repeated measure analysis for both primary and secondary endpoints, which allows for all participants with complete or partial data.

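### Section 8.5 lets sites take women off study for the same tolerability and adherence reasons for which 8.4 wants them kept, so primary-endpoint mammograms can be lost selectively

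*Combined protocol and SAP*

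**What the plan says.** Section 8.4 (Off-Agent Criteria) gives the reasons for stopping the gel. Apart from completing the intervention, they are "adverse event or serious adverse event, inadequate agent supply, noncompliance, concomitant medications, medical contraindication, or pregnancy". It then sets two retention rules: "Participants will continue to be followed, if possible, for safety reasons and in order to collect endpoint data according to the schedule of events", and "Women who discontinue the agent for any reason should continue on study if possible to allow for collection of their routine mammograms".

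Section 8.5 (Off-Study Criteria) says that participants may go off study once intervention and follow-up are complete, or for "adverse event/serious adverse event, lost to follow-up, non-compliance, concomitant medication, medical contraindication, withdraw consent, or death". It does not refer to 8.4 and does not ask that the mammogram be obtained first.

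Section 6.9 (Blinding and Unblinding Methods) includes, among the steps for breaking the blind before study completion, that the site investigator takes the woman off study. Unacceptable toxicity is one of its grounds for unblinding.

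On analysis, 13.4 says "The intent-to-treat population is defined as all participants who are randomized and have MD measurements from both baseline and 52 weeks", and that the comparison is made "per randomization, regardless of the compliance of each participant". If primary data are missing, 13.6 says that "the change of the primary endpoint will not be calculated, and the participant will not be evaluable for the primary endpoint". Section 13.8 requires every participant to be assessed for response, major deviations included.

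**The concern.** Stopping the agent and ending endpoint collection are separate decisions, and 13.4 depends on keeping them apart. A woman who stops the gel because of a reaction or poor adherence is one whom an analysis regardless of compliance must include. Section 8.4 tries to keep her; 8.5 allows a site to release her for the same reason. Both actions comply with the protocol, so seven sites can act differently.

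The four shared reasons are plausibly related to arm (tolerability) and to outcome (exposure to the gel). If they decide who has a second mammogram, the primary comparison moves towards women who tolerated and used the gel. The allowance for inevaluable women would also be spent on avoidable site decisions as well as on true loss.

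The analysis plan cannot repair this afterwards. Month 12 (or Month 13-18) is the first post-baseline mammogram in both schedules of events. A woman taken off study before then has only a baseline value, and a repeated-measures model learns nothing about her change. Multiple imputation in 13.6 is only to be considered, as a supplement, and assumes data missing at random. If most women who stop the gel leave, few observed stoppers remain on whom to base the imputation.

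**Working it through.** **1. The two lists side by side**

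| Reason | 8.4 off agent | 8.5 off study |
|---|---|---|
| Adverse event / SAE | yes | yes |
| Non-compliance | yes | yes |
| Concomitant medication | yes | yes |
| Medical contraindication | yes | yes |
| Inadequate supply, pregnancy | yes | no |
| Lost to follow-up, consent withdrawn, death | no | yes |

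Four reasons lead to either status, and no text chooses between them.

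**2. The plan's own figures (13.1)**

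Inputs: decreases of 6 and 2 points, SD 8, two-sided alpha 0.05, 80% power, 158 randomized 1:1, about 19% attrition.

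- Standardized difference = (6 − 2)/8 = 0.5. The two-sample t-test needs 63.8, so 64 per arm; power at 64 is 80.1%. Reproduced.
- 128/(1 − 0.19) = 158.02, against 158 stated. Reproduced.
- Allowance = 158 − 128 = 30, or 79 − 64 = 15 per arm.
- Section 8.4 instead states 7 per arm: 64 + 7 = 71 per arm, 142 in total. This does not match 158.

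The allowance protects power against loss. It does not protect the estimate against selective loss.

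**3. Illustration of size (assumptions not in the documents)**

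Suppose *k* of the 79 active-arm women leave for the four reasons and, being off gel, would have changed by −2. The others change by −6 and placebo by −2.

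- Complete-case difference = 6 − 2 = 4.0, whatever *k* is.
- Difference regardless of compliance = 4 × (79 − k)/79.
- Ratio of the two = 79/(79 − k).
- Share of the active arm's allowance = k/15.

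| k (share of 79) | Difference regardless of compliance | Complete-case excess | Share of 15 |
|---|---|---|---|
| 4 (5%) | 3.80 | 5% | 27% |
| 8 (10%) | 3.59 | 11% | 53% |
| 12 (15%) | 3.39 | 18% | 80% |
| 16 (20%) | 3.19 | 25% | 107% |

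At k = 16 the active arm falls to 63, below the planned 64, before any other loss.

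**4. Sensitivity to the assumptions**

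- Placebo losses: if stopping placebo gel does not alter the change, the placebo mean is −2 with or without the leavers, and the table stands.
- Partial effect: if leavers keep half of the 4-point effect, the difference regardless of compliance is 4 × (79 − k/2)/79, which is 3.90 at k = 4 and 3.59 at k = 16.
- If leavers change as much as completers, there is no bias. If they change more, the complete-case figure is too small.

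**The case against.** The case against is that the protocol already intends retention. Section 8.5 is permissive and directs no removal. Section 8.4 keeps women for any reason of stopping, and 13.8 wants everyone assessed. Section 5.5 takes women with toxicity off study drug, not off study. The COVID-19 Contingency Plan takes women who decline extended gel off agent and asks to collect their next mammogram. Section 8.5 can then be read as the list of outcomes when staying is not possible, which the qualifier in 8.4 leaves open. Nor does 8.5 say that image collection stops: the mammograms are standard of care, and at Month 24 staff collect images without approaching the woman (Section 3).

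Much of this stands. A reader might infer that mammograms are in fact being lost selectively, or that the effect will be overstated by 5% to 25%. The documents support neither. They give no number of women taken off study for these reasons, no outcome for women who stop, and no direction of bias. The illustration assigns leavers a fully placebo-like change, with no credit for months of gel use. That off-study status ends image collection is a natural reading, since the list also contains completed follow-up, loss, withdrawal of consent and death, but it is an inference.

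What does not fall away is the ambiguity. Nothing in 8.5 limits the four reasons to women who cannot be followed, and 6.9 is written as a directive. A site that ends participation for non-compliance has broken no rule.

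**Conclusion.** The point holds as a conflict between follow-up rules that bears on the primary endpoint. Sections 8.4 and 8.5 attach opposite consequences to the same four reasons, 6.9 adds an off-study step after unblinding, and neither 8.5 nor 6.9 fits 13.4 and 13.8. Because the primary set is complete-case, mammograms can be lost for reasons related to tolerability and adherence.

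The size is unknown. Under the stated assumptions (5% to 20% of the active arm leaving, fully placebo-like change), 4.0 points would compare with 3.80 to 3.19, and the leavers would take 27% to 107% of about 15 places. These figures show why the wording matters; they are not an estimate for this trial. The sample-size calculation reproduces and is not in question, apart from the mismatch with the 7 per arm in 8.4. The sponsor should act because the loss is avoidable and the remedy cheap.

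**What to change.** Reconcile 8.4, 8.5 and the off-study step in 6.9 so that neither stopping the agent nor unblinding by itself ends endpoint collection. In 8.5, state that a woman off agent for adverse event/SAE, non-compliance, concomitant medication or medical contraindication stays on study for collection of her standard-of-care Month 12 (or Month 13-18) and Month 24 mammograms, unless she withdraws consent, is lost to follow-up or dies. Make the same statement in 6.9; editing 8.5 alone would leave that route open. Align the 7 per arm in 8.4 with the allowance in 13.1.

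Leave unchanged the rules for stopping the gel, safety management and the pregnancy follow-up in 7.3 and 7.4.

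The cost is a few paragraphs of protocol wording and a few more images to collect and read; no procedure is added. Women retained after stopping may dilute the observed difference. Under the illustration, with SD 8 and all 79 per arm measured, power would be 84% if 5% stop and 72% if 19% stop. That dilution belongs to the question 13.4 asks.

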## 8.6 Study Termination

NCI, DCP as the study sponsor has the right to discontinue the study at any time.

## 9. CORRELATIVE/SPECIAL STUDIES

### 9.1 Rationale for Methodology Selection

Section 8 outlines our primary and secondary endpoint biomarkers. The primary endpoint measurement will be done by assessing MD using standard clinical methods. For secondary endpoints, again, we choose methods that have been previously published, either by our group or other investigators, that are widely available, practical, and financially preferable.

## 9.2 Comparable Methods

The methodologies described above are those previously used (see details above), and the resulting data will be able to be compared to existing data.

## 10. SPECIMEN MANAGEMENT

### 10.1 Laboratories

10.1.1 4-OHT metabolite analysis will be performed at the IIT Research Institute, Chicago, IL in plasma and in tissue.

10.1.2 F VIII, vWB factor, SHBG, lipid profile, CRP, and estradiol will be performed at UT MD Anderson Outpatient Laboratory.

10.1.3 Plasma IGF pathway biomarkers will be performed in [name] research laboratory.

10.1.4 Exploratory tissue biomarkers (TDLU involution; collagen structural changes; SETER/PR index: estrogen related transcription; Ki-67, COX-2, p16, and CD68) will be performed by our pathology collaborator, [name] in the Departments of Pathology and Translational Molecular Pathology at UT MD Anderson Cancer Center.

### 10.2 Collection and Handling Procedures

Note: data from Month 13-18 visit instead of Month 12 visit will be used if participants were seen under the COVID-19 Contingency Plan. If data were not collected at Month 6 under the COVID-19, such participants will have missing data.

#### Submission of mammographic data Using TRIAD

TRIAD is the American College of Radiology's (ACR) image exchange application. TRIAD provides sites participating in clinical trials a secure method to transmit DICOM RT and other objects. TRIAD anonymizes and validates the images as they are transferred.

#### TRIAD Access Requirements

Site staff who will submit images through TRIAD will be provided necessary log in information. To submit images, the site staff must be on the delegation of task log and be assigned the 'TRIAD site user' role.

#### TRIAD Installations

The TRIAD site user will need to have the TRIAD application installed on his/her workstation to be able to submit images.

TRIAD installation documentation can be found by following this link

<https://triadinstall.acr.org/triadclient/>

If you have any questions regarding this information, please send an e-mail to the TRIAD Support mailbox at [contact].

#### Procedures for Data Submission via TRIAD

Mammograms with their corresponding Diagnostic Imaging Report should be submitted for each participant in this study at the following time points:

1. The original mammogram taken at most 3 months prior to registration.
2. The mammogram taken as near as possible to one year after registration;
3. The mammogram taken as near as possible to two years after registration.

**Submission of mammographic data**

Digital mammography systems produce images in two forms, commonly referred to as the ‘raw’ image and the ‘processed’ images. For analysis of mammographic density **raw images** will be required, both raw images and ‘processed’ images will be collected.

All centers involved perform Digital Breast Tomography. As the current standard for 3D digital breast tomography is to include 3D images and either a conventional dose 2D mammogram or a synthesized 2D image, both the 3D and 2D images should be submitted. Only the 3D images will be analyzed, but 2D images will also be collected to create a data resource for future studies.

Digital files must be in DICOM format. Ensure that software used to de-identify images does not remove the date of the scan and specifics of the physics/image acquisition such as breast thickness and compression.

These files may be submitted electronically preferably with TRIAD. Alternatively, the images and reports may be submitted via secure portal to UT MD Anderson.

Research Blood collection:

Peripheral blood will be obtained by venipuncture at baseline, at 6 and at 12 months.

For the purpose of tracking samples: a pre-printed label will be attached to identify all sample vials.

Approx. 25 mL of blood will be collected and processed as per the Laboratory Manual. Refer to the Laboratory Manual for storage instructions.

Breast Core Biopsy (see also section 7.6):

The breast core biopsy (image guided) is optional. A 14-gauge needle will be used. Every effort will be made to collect 4 cores of tissue, with the minimum of 2 cores per participant at each time point.

Tissue will be considered adequate for research assays if the H&E stained slide from the block demonstrates at least one TDLU in every tissue core. One H&E slide will be prepared for adequacy and histological assessment. Usually each TDLU contains 200 to 2500 cells. If no TDLUs are seen, deeper sections will be obtained. Subsequent slides will be used for biomarker analysis.

- Samples should be collected and processed in the order below:

Breast Biopsy Sample Priority:	
Sample 1	FF
Sample 2-3	PE
Sample 4	RNALater®

- **Flash Frozen (FF) sample:** Biopsy sample (#1) should be placed directly into pre-labeled cryovial and snap frozen on isopentane, or liquid nitrogen, and then temporary storage on dry ice for transport to freezer at -80°C for storage.
  - If the institution does not have access to isopentane, liquid nitrogen may be used.

- Snap freeze your samples in liquid nitrogen and put them in a cool rack on dry ice for transport to freezer.
- **Paraffin Embedded (PE) samples:** Two core specimens (#2 and #3) will be placed in a pre-labeled container of 10% formalin for a maximum of 24-72 hours prior to embedding and processed using standard institutional procedures.
  - The minimum number of biopsies required is 2.
    - If this is the case, Sample 1 will be flash frozen and Sample 2 will be paraffin embedded.
- **RNA Later® sample:** Biopsy sample (#4) should be placed directly into a pre-labeled cryovial containing 5-10 volumes of RNA later® (we pre-aliquoted at 1.25ml per tube), tube with sample should be placed at 4°C for at least 24 to 72hrs, then transfer to -80°C for long term storage before it's shipped to MD Anderson on dry ice.

### 10.3 Shipping Instructions

All samples will be shipped in compliance with the International Air Transport Association (IATA) Dangerous Goods Regulations.

All research specimens will be shipped to the laboratory of the Principal Investigator, [name]. The laboratory is equipped with -80 degree freezers which serve as repositories for research samples. Ship all specimens to the address below:

[name]  
[name]  
[name]  
[name]  
Direct [contact]  
Email: [[contact]](mailto:[contact])

Use **Appendix I:** Specimen Inventory Form when shipping specimens. Fill Out One Form Per Patient, Per Time-Point.

Do not ship on Thursday, Friday or the day prior to a public holiday.

### 10.4 Tissue Banking

Biologic specimens collected during the conduct of this clinical trial that are not used during the course of the study will be considered deliverables under the contract and thus the property of the NCI. At study completion, NCI reserves the option to either retain or relinquish ownership of the unused biologic specimens. If NCI retains ownership of specimens, the Contractor shall collect, verify and transfer the requested biologic specimens from the site to a NCI-specified repository or laboratory at NCI's expense.

